**In the event of treatment-emergent Hypertension:**

Grade of hypertension Event (CTCAE v.3)	Management/ Next Dose
grade 1	Consider increased BP monitoring
grade 2 asymptomatic and diastolic BP < 110 mm Hg	Begin anti-hypertensive therapy and continue agent
grade 2 symptomatic/ persistent OR diastolic BP ≥ 110 mm Hg OR grade 3	1. Agent should be held* until symptoms resolve and diastolic BP ≤ 100 mm Hg; also treat patient with anti-hypertensives and restart at reduced dose of 600 mg/day given as 400 mg in the AM and 200 mg in the PM. Dose can be re-escalated to full dose as tolerated. 2. If diastolic BP not controlled (≤ 100 mm Hg) on therapy, reduce to another dose level with a dose of 400 mg/day given as 200 mg in the AM and 200 mg in the PM. **
grade 4	Discontinue protocol therapy

\* Patients requiring a delay of > 3 weeks should go off protocol therapy.  
\*\* Patients requiring > 2 dose reductions should go off protocol therapy.

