## **4 TREATMENT PLAN**

### **4.1 Sorafenib (BAY 43-9006) Administration**

Treatment will be administered on an outpatient basis. Reported adverse events and potential risks are described in [Section 6](#). Appropriate dose modifications for sorafenib (BAY 43-9006) are described in [Section 5](#). No investigational or commercial agents or therapies other than those described below may be administered with the intent to treat thyroid cancer.

Sorafenib (BAY 43-9006) will be administered at the dose of 400 mg orally twice a day on a continuous basis. Sorafenib (BAY 43-9006) is supplied as 200-mg tablets. Patients are to swallow the tablets whole with approximately 250 ml (8 oz.) of water, each morning and evening (i.e., approximately 12-hourly). When given with a moderate fat meal, bioavailability was similar to that in the fasted state. With a high fat meal, sorafenib (BAY 43-9006) tosylate's bioavailability was reduced by 29% compared to administration in the fasted state. Thus, it is recommended that sorafenib (BAY 43-9006) be taken on an empty stomach (at least 1 hour before or 2 hours after eating).

Patients will be given monthly calendars (patient diaries) to document the time when the sorafenib (BAY 43-9006) pills are taken. At monthly visits, patients will bring back this record.

Hypertension is a known and potentially serious adverse event associated with Sorafenib (BAY 43-9006) treatment. Patients will have their blood pressure monitored and recorded weekly during the first cycle of therapy, either at the doctor's office or using any calibrated electronic device (such as those found at a local drug store or pharmacy). Patients will be provided with a Blood Pressure Check Diary on which to record the measurements. An increase in blood pressure of > 20 mm Hg (systolic) and 10 mm Hg (diastolic) should be reported to the treating physician immediately. See dose modification guidelines in section 5 in event of drug related hypertension.

Oral or intravenous (IV) bisphosphonates therapy will be allowed for patients with bony metastasis at the investigator's discretion.

Close monitoring is recommended for patients taking BAY 43-9006 tosylate and CYP3A4 inducers. The CYP3A4 inducers such as antiepileptic drugs (phenytoin, carbamazepine, or Phenobarbital), rifampin or St. John's Wort are not permitted on the protocol due to potential drug interactions with sorafenib.

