**Dose should be modified and/or delayed according to the following guidelines:**

**In the event of grade 3 or 4 drug-related non-hematologic toxicity**, therapy will be held till the toxicity has resolved to baseline or  $\leq$  grade 1. For delay of treatment due to toxicity for more than 21 consecutive days, patient will be removed from the study. Once toxicity is resolved to baseline or  $\leq$  grade 1, sorafenib (BAY 43-9006) should be started at a reduced dose of 200 mg PO BID. If tolerated, the dose can be re-escalated to 600 mg/day given as 400 mg in the AM and 200 mg in the PM. If 600 mg/day dose is tolerated, further re-escalation to the full dose of 400 mg PO BID may be done after discussing with protocol chair.

**In the event of grade 2 hand-foot skin reaction or recurrent grade 2 drug-related non-hematologic toxicity**, therapy may be held till the toxicity has resolved to baseline or  $\leq$  grade 1. For delay of treatment due to toxicity for more than 21 consecutive days, patient will be removed from the study. Once toxicity is resolved to baseline or  $\leq$  grade 1, sorafenib (BAY 43-9006) should be started at a reduced dose of 200 mg PO BID. If tolerated, the dose can be re-escalated to 600 mg/day given as 400 mg in the AM and 200 mg in the PM. If 600 mg/day dose is tolerated, further re-escalation to the full dose of 400 mg PO BID may be done after discussing with protocol chair.

**In the event of GI-Perforation**, patient will be removed from the study and followed until adverse event is resolve.

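### The fixed 600 mg/day restart after hypertension is no reduction, or an increase, for a patient already below full dose

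*Combined protocol and SAP*

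**What the plan says.** Section 4.1 starts every patient on 400 mg twice daily, that is 800 mg/day. Section 5 then has two sets of dose rules.

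- **Non-hematologic toxicity in general.** After grade 3 or 4 events, and also "In the event of grade 2 hand-foot skin reaction or recurrent grade 2 drug-related non-hematologic toxicity", drug is held until recovery and then "should be started at a reduced dose of 200 mg PO BID. If tolerated, the dose can be re-escalated to 600 mg/day". The last step back is discretionary: "further re-escalation to the full dose of 400 mg PO BID may be done after discussing with protocol chair".
- **Treatment-emergent hypertension.** The third row of the table opens with "grade 2 symptomatic/ persistent OR diastolic BP" of 110 mm Hg or more, and also takes in grade 3. Nothing in that trigger refers to the dose the patient is taking. Step 1 is to hold, give antihypertensives, and, once symptoms have resolved and diastolic pressure is at most 100 mm Hg, "restart at reduced dose of 600 mg/day given as 400 mg in the AM and 200 mg in the PM". Step 2, for diastolic pressure not controlled on therapy, is to "reduce to another dose level with a dose of 400 mg/day given as 200 mg in the AM" and the same in the evening. A footnote adds: "Patients requiring > 2 dose reductions should go off protocol therapy".

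**The concern.** Step 1 names an absolute dose where the purpose calls for a relative one. It works for a patient on full dose. For a patient already at 600 mg/day it changes nothing, and for a patient at 400 mg/day it raises the dose straight after a hold for toxicity. Section 4.1 says of this event: "Hypertension is a known and potentially serious adverse event associated with Sorafenib (BAY 43-9006) treatment".

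What is at stake is the safety of a few patients and consistent dosing across sites. Blood-pressure follow-up also thins with time. The Study Calendar asks for weekly readings until stable or for at least the first 4 weeks, and after six months evaluation visits are 16 weeks apart. A late restart at too high a dose could therefore receive little protocol-required monitoring.

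**Working it through.** The plan states no figure to reproduce here. The check is daily-dose arithmetic over the dose levels that Section 5 allows.

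**Inputs**
- Full dose: 2 x 400 = 800 mg/day (Section 4.1).
- Dose after another toxicity: 2 x 200 = 400 mg/day, with optional return to 600 and then 800 mg/day (Section 5, general rules).
- Hypertension, third row: step 1 = 400 + 200 = 600 mg/day; step 2 = 200 + 200 = 400 mg/day (Section 5, table).

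**Can a patient be below 800 mg/day when hypertension occurs?** Yes. The general rules restart at 400 mg/day. Both steps back up are permitted, not required, and the last needs discussion with the protocol chair. They never drop a patient directly to 600; that level is reached by partial re-escalation.

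**Change in daily dose = prescribed dose / dose before the hold - 1**

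| Dose before hold (mg/day) | Step 1 (600 mg/day) | Step 2 (400 mg/day) |
|---|---|---|
| 800 | 600/800 - 1 = -25% | follows step 1 |
| 600 | 600/600 - 1 = 0% | 400/600 - 1 = -33.3% |
| 400 | 600/400 - 1 = +50% (+200 mg/day, one tablet) | 400/400 - 1 = 0% |

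**Does step 2 repair step 1?** Partly. It lowers a patient on 600 whose diastolic pressure stays above 100 mm Hg. It does not reach a patient on 600 who entered the row through symptoms with diastolic pressure at or below 100. For a patient who was on 400, it only brings the dose back to where it was.

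**Does the cap on reductions remove these patients?** Counting by event, one reduction for the earlier toxicity plus one for hypertension is 2, which does not exceed 2.

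**How many patients?** Section 6.2 lists hypertension in the class of at most 20%. I take that as covering all grades and as applying to this population; the section states neither.
- Upper figure for any hypertension: 0.20 x 50 = 10 overall, or 0.20 x 25 = 5 per arm.
- Share of those at a reduced dose for another toxicity: not in the documents. I assume 10% to 35.5%. The upper end is the hand-foot skin reaction rate at this dose in Section 2.5 (11 patients; 11/0.355 = 31 treated), which is not split by grade.
- Result: 10 x 0.10 = 1.0 to 10 x 0.355 = 3.55, so about 1 to 4 of 50 before restricting to third-row events.

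**The case against.** The strongest reply is that no sensible investigator would read the table this way. Step 1 calls its dose reduced, and the general rules allow a move from 400 to 600 mg/day only if the lower dose is tolerated. The intent is plain, but the wording does not secure it. The general rules also call 200 mg twice daily a reduced dose, and that is no reduction for a patient already taking it. No text bars a restart above the dose before the hold.

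Second, drug-related grade 3 hypertension also fits the general grade 3 or 4 rule, which gives 400 mg/day. Section 5 does not say which rule prevails. The point does not depend on settling that, because a first symptomatic grade 2 event triggers only the table.

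Third, the footnote could count dose levels instead of events. Going from 800 to 400 would then use two reductions, and a patient at 400 needing another would leave therapy. That reading is possible but not stated, and it leaves step 1's instruction to restart at 600 uncorrected.

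Fourth, restarting at 600 after 600 may be defensible: pressure is controlled, antihypertensives are in use, and the second row continues the drug unchanged for milder hypertension. This carries some weight, and it is why the 600 case is the weaker of the two. Yet the third row prescribes a step down for its own, more serious events, and its ladder runs 800, 600, 400. Going from 600 to 400 applies that ladder.

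The patient count is indeed soft. It is an upper class limit multiplied by an assumed share.

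**Conclusion.** The concern holds, as a minor one. Step 1 is correct only from 800 mg/day. Followed as written, it gives no reduction from 600 mg/day and a 50% increase from 400 mg/day, and from 400 mg/day neither step lowers the dose. The dose arithmetic needs no assumption beyond Section 5; the 1 to 4 of 50 rests on the assumptions given with it.

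The practical effect is limited. It requires an earlier reduction for another toxicity, no return to full dose, and then a third-row event. Blood pressure must be controlled before restart, step 2 covers part of the gap, Section 4.3 allows stopping for unacceptable toxicity, and Section 10.1.4 provides review at least monthly. The objective response endpoint and the 16/25-patient two-stage design are not affected.

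**What to change.** Reword step 1 of the third row so that treatment restarts one dose level below the dose taken before the hold: 800 to 600 mg/day (-25%) and 600 to 400 mg/day (-33.3%). For a patient held at 400 mg/day, state that restart is at no more than 400 mg/day or that the patient goes off therapy, as the sponsor's clinicians decide.

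This uses only dose levels already in Section 5 and leaves the full-dose case as it is. The cost is a short amendment to one table cell and a restart dose 200 mg/day lower in a few patients. No patients, visits or procedures are added.

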**6 PHARMACEUTICAL INFORMATION****6.1 Sorafenib (BAY 43-9006) (NSC 724772)**

**Chemical Name:** 4-{4-[3-(4-chloro-3-trifluoromethyl-phenyl) ureido]-phenoxy} pyridine-2 carboxylic acid methylamide-4-methylbenzenesulfonate.

**Other names:** BAY 54-9085 is the tosylate salt of BAY 43-9006; sorafenib; Nexavar®.

**Molecular Formula:** C12H16ClF3N4O3 × C7H8O3S

**M.W.:** BAY 43-9006 tosylate: 637 Daltons; BAY 43-9006 (free base): 465 Daltons

**Classification:** Kinase inhibitor (Raf, VEGF-R, and PDGF-R).

**Description:** The ras/raf signaling pathway is an important mediator of responses to growth signals and angiogenic factors. This pathway is often aberrantly activated in human tumors due to presence of activated ras, mutant b-raf, or over expression of growth factor receptors. BAY 43-9006 is a potent inhibitor of c-raf, and wild-type and mutant b-raf in vitro. Additionally, further characterization of BAY 43-9006 tosylate revealed that this agent inhibits several receptor tyrosine kinases (RTKs) that are involved in tumor progression (VEGF-R, PDGF-R, Flt3, and c-KIT) and p38α, a member of the MAPK family.

**How Supplied:** Sorafenib tosylate is supplied by Bayer Healthcare AG and distributed by PMB, CTEP, DCTD, NCI. The tablets are available as 200 mg immediate release tablets. The inactive ingredients are microcrystalline cellulose, croscarmellose sodium, hydroxypropylmethyl cellulose, magnesium stearate, sodium lauryl sulfate, and a film-coat with hydroxypropylmethylcellulose, polyethylene glycol, titanium dioxide and red iron oxide.

■ The commercially labeled 200 mg tablets are round, biconvex, red film-coated tablets, debossed with the “Bayer cross” on one side and “200” on the other side and packaged in HDPE bottles of 120 tablets.

NOTE: Sorafenib tablets may be repackaged in HDPE pharmacy dispensing bottle other than the original container with expiration date not to exceed 30 days.

**Route of Administration:** Orally.

**Method of Administration:** Following oral administration, sorafenib (BAY 43-9006) tosylate's mean relative bioavailability is 38-49%. When given with a moderate fat meal, bioavailability was similar to that in the fasted state. With a high fat meal, BAY 43-9006 tosylate's bioavailability was reduced by 29% compared to administration in the fasted state. Thus, it is recommended that sorafenib (BAY 43-9006) be taken on an empty stomach (at least 1 hour before or 2 hours after eating) and with at least 250 mL of water.

**Drug Product Storage:** Store intact bottles at controlled room temperature, not to exceed 25°C.

If a storage temperature excursion is identified, promptly return sorafenib to controlled room temperature (not to exceed 25°C) and quarantine the supplies. Provide a detailed report of the excursion (including documentation of temperature monitoring and duration of the excursion) to [contact] for determination of suitability.

**Drug Product Stability:** Stability studies are ongoing for investigationally-labeled supplies. Refer to package labeling for shelf life of commercially-labeled supplies.

**Approximate Solubility:** 0.19 mg/100 mL in 0.1 N HCl, 453 mg/100 mL in Ethanol, and 2971 mg/100 mL in PEG 400.

**Potential Drug Interactions:** Sorafenib metabolizes primarily by CYP3A4 during phase I metabolism (oxidation) and primarily by UGT1A9 in phase II (conjugation). Co-administration of rifampin resulted in sorafenib AUC reduction of approximately 37%. Therefore, use caution when co-administering with strong CYP3A4 inducers, such as St. John's wort, phenytoin, carbamazepine, phenobarbital and dexamethasone as they can reduce sorafenib exposure. CYP3A4 inhibitors are not expected to cause clinically relevant changes to sorafenib exposure.

In vitro, sorafenib is a moderate inhibitor CYP2C19, 2D6, and 3A4 and a strong inhibitor of CYB2B6, 2C8, and 2C9. It also inhibits pathway enzymes UGT1A1 and UGT1A9 in phase II conjugation. Clinical data suggests sorafenib does not increase exposure of other drugs metabolized by CYP pathways and therefore does not appear to be clinically relevant. Use caution when co-administered with sensitive substrates of UGT1A1.

While sorafenib solubility is pH dependent, co-administration with omeprazole did not result in clinically relevant change in sorafenib exposure.

Sorafenib may prolong the QT/QTc interval. Avoid concomitant drugs that may induce the QTc prolongation.

**Patient Care Implications:** Hand-foot skin rash can be treated with topical emollients, high-potency topical steroids, or keratolytic cream (urea/salicyclic acid).

Females of childbearing potential should avoid becoming pregnant while they or their male partners are taking sorafenib and should use effective contraception during and for at least 30 days after completion of therapy.

#### **Availability:**

Sorafenib (BAY 43-9006) is an investigational agent supplied to investigators by the Division of Cancer Treatment and Diagnosis (DCTD), NCI.

Sorafenib (BAY 43-9006) is provided to the NCI under a Clinical Trials Agreement (CTA) between Bayer Corp./Onyx and the DCTD, NCI (see Section 10.4).

#### **Agent Ordering and Agent Accountability**

NCI-supplied agents may be requested by the Principal Investigator (or their authorized designee) at each participating institution. Pharmaceutical Management Branch (PMB) policy requires that agent be shipped directly to the institution where the patient is to be treated. PMB does not permit the transfer of agents between institutions (unless prior approval from PMB is obtained). The CTEP-assigned protocol number must be used for ordering all CTEP-supplied investigational agents. The responsible investigator at each participating institution must be registered with CTEP, DCTD through an annual submission of FDA Form 1572 (Statement of Investigator), Curriculum Vitae, Supplemental Investigator Data Form (IDF), and Financial Disclosure Form (FDF). If there are several participating investigators at one institution, CTEP-supplied investigational agents for the study should be ordered under the name of one lead investigator at that institution.

In general, sites may order initial agent supplies when a subject is being screened for enrollment onto the study.

Active CTEP-registered investigators and investigator-designated shipping designees and ordering designees can submit agent requests through the PMB Online Agent Order Processing (OAOP) application. Access to OAOP requires the establishment of a CTEP Identity and Access Management (IAM) account and the maintenance of an “active” account status and a “current” password. For questions about drug orders, transfers, returns, or accountability, call or email PMB any time. Refer to the PMB’s website for specific policies and guidelines related to agent management.

#### **Agent Inventory Records**

The investigator, or a responsible party designated by the investigator, must maintain a careful record of the receipt, dispensing and final disposition of all agents received from the PMB using the appropriate NCI Investigational Agent (Drug) Accountability Record (DARF) available on the

CTEP forms page. Store and maintain separate NCI Investigational Agent Accountability Records for each agent, strength, formulation and ordering investigator on this protocol.

### **Investigator Brochure Availability**

The current versions of the IBs for the agents will be accessible to site investigators and research staff through the PMB Online Agent Order Processing (OAOP) application. Access to OAOP requires the establishment of a CTEP Identity and Access Management (IAM) account and the maintenance of an “active” account status and a “current” password. Questions about IB access may be directed to the PMB IB coordinator via email.

## **6.2 Comprehensive Adverse Events and Potential Risks list (CAEPR) For Sorafenib (BAY 43-9006, NSC 724772)**

The Comprehensive Adverse Events and Potential Risks list (CAEPR) provides a single list of reported and/or potential adverse events (AE) associated with an agent using a uniform presentation of events by body system. In addition to the comprehensive list, a subset, the Specific Protocol Exceptions to Expedited Reporting (SPEER), appears in a separate column and is identified with bold and italicized text. This subset of AEs (SPEER) is a list of events that are protocol specific exceptions to expedited reporting to NCI (except as noted below). Refer to the 'CTEP, NCI Guidelines: Adverse Event Reporting Requirements'

[http://ctep.cancer.gov/protocolDevelopment/electronic\\_applications/docs/aeguidelines.pdf](http://ctep.cancer.gov/protocolDevelopment/electronic_applications/docs/aeguidelines.pdf) for further clarification. *Frequency is provided based on 2571 patients.* Below is the CAEPR for Sorafenib (BAY 43-9006).

**NOTE:** Report AEs on the SPEER **ONLY IF** they exceed the grade noted in parentheses next to the AE in the SPEER. If this CAEPR is part of a combination protocol using multiple investigational agents and has an AE listed on different SPEERs, use the lower of the grades to determine if expedited reporting is required.

**Version 2.7, November 16, 2015**

Adverse Events with Possible Relationship to Sorafenib (BAY 43-9006) (CTCAE 4.0 Term) [n= 2571]			Specific Protocol Exceptions to Expedited Reporting (SPEER)
Likely (>20%)	Less Likely (<=20%)	Rare but Serious (<3%)	
BLOOD AND LYMPHATIC SYSTEM DISORDERS			
Anemia			Anemia (Gr 3)
CARDIAC DISORDERS			
		Acute coronary syndrome	
	Chest pain - cardiac		
		Heart failure	
		Left ventricular systolic dysfunction	
		Myocardial infarction	
GASTROINTESTINAL DISORDERS			
Abdominal pain			Abdominal pain (Gr 3)
	Ascites		
	Constipation		Constipation (Gr 2)
Diarrhea			Diarrhea (Gr 3)
	Gastrointestinal hemorrhage 		Gastrointestinal hemorrhage (Gr 3)
		Gastrointestinal perforation 	
	Mucositis oral		
Nausea			Nausea (Gr 3)
	Vomiting		Vomiting (Gr 3)
GENERAL DISORDERS AND ADMINISTRATION SITE CONDITIONS			
	Edema limbs		
Fatigue			Fatigue (Gr 3)
	Fever		Fever (Gr 2)
HEPATOBILIARY DISORDERS			
		Hepatic Failure	
IMMUNE SYSTEM DISORDERS			
		Anaphylaxis	
INFECTIONS AND INFESTATIONS			
	Infection 		
INVESTIGATIONS			

Adverse Events with Possible Relationship to Sorafenib (BAY 43-9006) (CTCAE 4.0 Term) [n= 2571]			Specific Protocol Exceptions to Expedited Reporting (SPEER)
Likely (>20%)	Less Likely (<=20%)	Rare but Serious (<3%)	
	Activated partial thromboplastin time prolonged		Activated partial thromboplastin time prolonged (Gr 2)
Alanine aminotransferase increased			Alanine aminotransferase increased (Gr 3)
Alkaline phosphatase increased			Alkaline phosphatase increased (Gr 3)
Aspartate aminotransferase increased			Aspartate aminotransferase increased (Gr 3)
Blood bilirubin increased			Blood bilirubin increased (Gr 3)
Creatinine increased			Creatinine increased (Gr 3)
	GGT increased	Electrocardiogram QT corrected interval prolonged	
INR increased			INR increased (Gr 3)
	Investigations - Other (bicarbonate-serum low)		
Lipase increased			Lipase increased (Gr 3)
Lymphocyte count decreased			Lymphocyte count decreased (Gr 3)
	Neutrophil count decreased		Neutrophil count decreased (Gr 4)
Platelet count decreased			Platelet count decreased (Gr 4)
Serum amylase increased			Serum amylase increased (Gr 3)
Weight loss			Weight loss (Gr 2)
White blood cell decreased			White blood cell decreased (Gr 4)
METABOLISM AND NUTRITION DISORDERS			
Anorexia			Anorexia (Gr 3)
Hyperglycemia	Hypercalcemia		Hyperglycemia (Gr 3)
	Hyperkalemia		Hyperkalemia (Gr 3)
	Hypernatremia		
Hypoalbuminemia			Hypoalbuminemia (Gr 3)

Adverse Events with Possible Relationship to Sorafenib (BAY 43-9006) (CTCAE 4.0 Term) [n= 2571]			Specific Protocol Exceptions to Expedited Reporting (SPEER)
Likely (>20%)	Less Likely (<=20%)	Rare but Serious (<3%)	
Hypocalcemia			Hypocalcemia (Gr 3)
	Hypoglycemia		Hypoglycemia (Gr 2)
	Hypokalemia		Hypokalemia (Gr 3)
Hyponatremia			Hyponatremia (Gr 3)
Hypophosphatemia			Hypophosphatemia (Gr 3)
MUSCULOSKELETAL AND CONNECTIVE TISSUE DISORDERS			
	Arthralgia		Arthralgia (Gr 3)
	Back pain		Back pain (Gr 3)
	Bone pain		
	Musculoskeletal and connective tissue disorder - Other (muscle spasm)		
	Myalgia		
	Pain in extremity		Pain in extremity (Gr 3)
NEOPLASMS BENIGN, MALIGNANT AND UNSPECIFIED (INCL CYSTS AND POLYPS)			
	Treatment related secondary malignancy		
NERVOUS SYSTEM DISORDERS			
	Dizziness		
	Headache		Headache (Gr 3)
		Intracranial hemorrhage	
		Reversible posterior leukoencephalopathy syndrome	
PSYCHIATRIC DISORDERS			
	Insomnia		
RENAL AND URINARY DISORDERS			
	Acute kidney injury		
RESPIRATORY, THORACIC AND MEDIASTINAL DISORDERS			
	Cough		Cough (Gr 2)
	Dyspnea		Dyspnea (Gr 3)
	Respiratory hemorrhage 		

Adverse Events with Possible Relationship to Sorafenib (BAY 43-9006) (CTCAE 4.0 Term) [n= 2571]			Specific Protocol Exceptions to Expedited Reporting (SPEER)
Likely (>20%)	Less Likely (<=20%)	Rare but Serious (<3%)	
	Voice alteration		
SKIN AND SUBCUTANEOUS TISSUE DISORDERS			
Alopecia			Alopecia (Gr 2)
	Dry skin		Dry skin (Gr 2)
Palmar-plantar erythrodysesthesia syndrome		Erythema multiforme	Palmar-plantar erythrodysesthesia syndrome (Gr 3)
	Pruritus		Pruritus (Gr 3)
Rash maculo-papular			Rash maculo-papular (Gr 3)
		Stevens-Johnson syndrome Toxic epidermal necrolysis	
VASCULAR DISORDERS			
	Hypertension		Hypertension (Gr 3)
		Thromboembolic event	

This table will be updated as the toxicity profile of the agent is revised. Updates will be distributed to all Principal Investigators at the time of revision. The current version can be obtained by contacting [[contact]](mailto:[contact]). Your name, the name of the investigator, the protocol and the agent should be included in the e-mail.

Gastrointestinal hemorrhage may include Anal hemorrhage, Cecal hemorrhage, Colonic hemorrhage, Duodenal hemorrhage, Esophageal hemorrhage, Esophageal varices hemorrhage, Gastric hemorrhage, Hemorrhoidal hemorrhage, Ileal hemorrhage, Intra-abdominal hemorrhage, Jejunal hemorrhage, Lower gastrointestinal hemorrhage, Oral hemorrhage, Pancreatic hemorrhage, Rectal hemorrhage, Retroperitoneal hemorrhage, and Upper gastrointestinal hemorrhage under the GASTROINTESTINAL DISORDERS SOC.

Gastrointestinal perforation may include Colonic perforation, Duodenal perforation, Esophageal perforation, Gastric perforation, Ileal perforation, Jejunal perforation, Rectal perforation, and Small intestinal perforation under the GASTROINTESTINAL DISORDERS SOC.

Infection may include any of the 75 infection sites under the INFECTIONS AND INFESTATIONS SOC.

Respiratory hemorrhage may include bronchopulmonary hemorrhage, epistaxis, laryngeal hemorrhage, mediastinal hemorrhage, pharyngeal hemorrhage, and pleural hemorrhage under the RESPIRATORY, THORACIC AND MEDIASTINAL DISORDERS SOC.

Febrile neutropenia is seen mostly in combination with other agents.

**Adverse events reported on sorafenib (BAY 43-9006; Nexavar) trials but for which there is insufficient evidence to suggest that there was a relationship possibility that sorafenib (BAY 43-9006; Nexavar) caused the adverse event:**

**BLOOD AND LYMPHATIC SYSTEM DISORDERS** - Blood and lymphatic system disorders - Other (Thrombotic microangiopathy [e.g., TTP or HUS]); Febrile neutropenia

**CARDIAC DISORDERS** - Atrial fibrillation; Atrial flutter; Cardiac arrest; Palpitations; Pericardial effusion; Pericarditis; Right ventricular dysfunction; Sinus bradycardia; Sinus tachycardia; Supraventricular tachycardia; Ventricular arrhythmia; Ventricular tachycardia

**EAR AND LABYRINTH DISORDERS** - Hearing impaired; Tinnitus

**ENDOCRINE DISORDERS** - Adrenal insufficiency; Hyperthyroidism; Hypothyroidism

**EYE DISORDERS** - Blurred vision; Cataract; Dry eye; Extraocular muscle paresis; Eye disorders - Other (color vision deficits); Eye disorders - Other (light to dark adaptation); Eye disorders - Other (retinal vein occlusion); Eye disorders - Other (retinal hemorrhage); Eye disorders - Other (visual field distortion); Flashing lights; Keratitis; Photophobia; Retinal detachment

**GASTROINTESTINAL DISORDERS** - Abdominal distension; Anal fistula; Anal mucositis; Anal pain; Anal ulcer; Cheilitis; Colitis; Colonic obstruction; Colonic ulcer; Dry mouth; Duodenal ulcer; Dyspepsia; Dysphagia; Enterocolitis; Esophageal pain; Esophagitis; Flatulence; Gastric ulcer; Gastritis; Gastroesophageal reflux disease; Gastrointestinal disorders - Other (diverticulitis); Gastrointestinal disorders - Other (small bowel NOS fistula); Gastrointestinal fistula; Hemorrhoids; Ileal fistula; Ileus; Oral pain; Pancreatitis; Proctitis; Rectal fistula; Rectal mucositis; Rectal obstruction; Rectal pain; Small intestinal obstruction; Stomach pain

**GENERAL DISORDERS AND ADMINISTRATION SITE CONDITIONS** - Chills; Edema face; Facial pain; Flu like symptoms; Localized edema; Multi-organ failure; Non-cardiac chest pain; Pain

**HEPATOBILIARY DISORDERS** - Cholecystitis; Hepatic hemorrhage; Hepatobiliary disorders - Other (biliary obstruction secondary to multiple biliary stones)

**IMMUNE SYSTEM DISORDERS** - Allergic reaction; Cytokine release syndrome; Immune system disorders - Other (systemic inflammatory response syndrome)

**INJURY, POISONING AND PROCEDURAL COMPLICATIONS** - Arterial injury; Fall; Fracture; Hip fracture; Vascular access complication; Wound complication; Wound dehiscence

**INVESTIGATIONS** - CPK increased; Cardiac troponin I increased; Cardiac troponin T increased; Cholesterol high; Ejection fraction decreased; Fibrinogen decreased; Investigations - Other (blood urea nitrogen high)

**METABOLISM AND NUTRITION DISORDERS** - Acidosis; Alkalosis; Dehydration; Hypermagnesemia; Hypertriglyceridemia; Hyperuricemia; Hypomagnesemia; Tumor lysis syndrome

**MUSCULOSKELETAL AND CONNECTIVE TISSUE DISORDERS** - Arthritis; Chest wall pain; Generalized muscle weakness; Joint range of motion decreased; Muscle weakness left-sided; Muscle weakness lower limb; Muscle weakness right-sided; Muscle weakness upper limb; Musculoskeletal and connective tissue disorders - Other (cramping); Myositis; Neck pain

**NEOPLASMS BENIGN, MALIGNANT AND UNSPECIFIED (INCL CYSTS AND POLYPS)** - Leukemia secondary to oncology chemotherapy; Myelodysplastic syndrome; Neoplasms benign, malignant and unspecified (incl cysts and polyps) - Other (tumor

hemorrhage); Tumor pain

**NERVOUS SYSTEM DISORDERS** - Ataxia; Cognitive disturbance; Depressed level of consciousness; Dysgeusia; Dysphasia; Encephalopathy; Extrapyramidal disorder; Hydrocephalus; Ischemia cerebrovascular; Lethargy; Leukoencephalopathy; Memory impairment; Neuralgia; Peripheral motor neuropathy; Peripheral sensory neuropathy; Seizure; Stroke; Syncope; Tremor; Vasovagal reaction

**PSYCHIATRIC DISORDERS** - Agitation; Anxiety; Confusion; Depression; Libido decreased; Personality change; Psychosis

**RENAL AND URINARY DISORDERS** - Chronic kidney disease; Hematuria; Proteinuria; Renal and urinary disorders - Other (focal segmental glomerulosclerosis); Renal and urinary disorders - Other (nephrotic syndrome); Renal and urinary disorders - Other (right ureter rupture); Renal calculi; Renal hemorrhage; Urinary frequency; Urinary incontinence; Urinary retention; Urinary tract obstruction; Urine discoloration

**REPRODUCTIVE SYSTEM AND BREAST DISORDERS** - Erectile dysfunction; Gynecomastia; Hematosalpinx; Menorrhagia; Ovarian hemorrhage; Prostatic hemorrhage; Spermatic cord hemorrhage; Testicular hemorrhage; Uterine hemorrhage; Vaginal fistula; Vaginal hemorrhage

**RESPIRATORY, THORACIC AND MEDIASTINAL DISORDERS** - Adult respiratory distress syndrome; Allergic rhinitis; Bronchospasm; Hiccups; Hoarseness; Hypoxia; Laryngeal mucositis; Pharyngeal mucositis; Pharyngolaryngeal pain; Pleural effusion; Pneumonitis; Pneumothorax; Pulmonary edema; Pulmonary fibrosis; Respiratory, thoracic and mediastinal disorders - Other (nasal septal perforation); Tracheal mucositis

**SKIN AND SUBCUTANEOUS TISSUE DISORDERS** - Erythroderma; Hyperhidrosis; Nail loss; Pain of skin; Purpura; Rash acneiform; Scalp pain; Skin and subcutaneous tissue disorders - Other (folliculitis); Skin and subcutaneous tissue disorders - Other (non-life threatening squamous cell carcinoma of skin: keratoacanthoma type); Skin hyperpigmentation; Skin hypopigmentation; Skin ulceration; Urticaria

**VESTIBULAR DISORDERS** - Flushing; Hematoma; Hot flashes; Hypotension; Phlebitis; Vascular disorders - Other (ruptured aortic aneurysm); Vascular disorders - Other (visceral arterial ischemia); Vasculitis

**Note:** Sorafenib (BAY 43-9006) in combination with other agents could cause an exacerbation of any adverse event currently known to be caused by the other agent, or the combination may result in events never previously associated with either agent.

